#### 8.4.5 Additional Endpoints

- Proportion of successful single injections out of total number of single injections using the MOD-4023 PEN in US patients at Wks 1, 2, 3, 4, 5, and 6, based on the PAT.
- Proportion of successful single injections out of total number of single injections using the MOD-4023 PEN in US patients at Wk 1, based on the OAT.
- Comments on the PAT related to successful or unsuccessful injection attempts.
- Comments on the OAT related to successful or unsuccessful injection attempts.
- Information gained by inspection of returned devices.
- QoL endpoint measured by the QoLISSY core questionnaire at Baseline and month 12 at specific countries per [Appendix L](#).

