#### 8.6.4 Additional Endpoints Analysis

##### OAT and PAT (USA Patients Only)

OAT and PAT results will be summarized by using descriptive statistics.

The number and percentage of successful single injections for PAT will be summarized overall. A successful single injection for PAT will be based on the questions “Did the dose window show ‘0’ when you finished your injection?” and “Do you believe that a full dose was injected?” The single

injection is considered successful if the subject answers “Yes” to both questions for all attempts on the form. A subject can have multiple successful single injections at one visit.

Intermittent missing observations for the PAT will be imputed as a failure if both the prior and subsequent observations are a failure. Otherwise, intermittent missing observations will be imputed as a success.

The number and percentage of successful single injections for OAT will be summarized overall. A successful single injection for OAT will be based on the question “...did the user successfully inject into an acceptable injection site without physical assistance?” The single injection is considered successful if the observer answers “Yes” to the question for all attempts on the form. A subject can have multiple successful single injections at 1 visit.

The number and percentage of successful single injections for PAT and OAT will also be summarized by age group, sex, and race.

The number and percentage of the number of attempts required to achieve a success will be summarized for PAT and OAT.

Comments on the PAT and OAT related to successful or unsuccessful injection attempts will be listed.

Information gained by inspection of returned devices will be listed.

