**APPENDIX M: PARTICIPANT ASSESSMENT TOOL (PAT)**

**Patient Questionnaire** (only to be completed by the pen user)

Please complete a new questionnaire each time you take your dose of medicine.  
If splitting your dose between 2 different pens please complete a new questionnaire for each pen.  
It is important that the answers are given by the person who actually operated the pen.

Subject number

Subject ID

What day did you use the pen?

Date

What is the pen kit number?

Pen kit number

Have you used this pen before now? (ie. the pen is already in use)

Yes  No

**1** Who actually gave the injection?

- Subject       A Healthcare Professional  
 A relative or friend  
 Someone else (please specify)

I had help from: \_\_\_\_\_

**2** Were the instructions clear enough for you to use without getting any help?

Yes       No      I had help from: \_\_\_\_\_

Please check which instruction step(s) you had trouble with, below.

- | Preparing                                   | Priming  | Injecting                                     |
|---|--|---|
|  4 - Check medicine |  8 - Set priming dose  |  14 - Inject medicine |
|  5 - Attach needle  |  9 - Move air bubbles  |   |
|   |  10 - Press button     |   |
|   |  11 - Check for liquid |  Other                |

Please state why: \_\_\_\_\_

**3** Which area did you try to inject?

- Thigh       Abdomen       Arm       Buttock

Effective Date: Date of final electronic approval

4 How many injections did you take from this pen today?

1 injection

2 injections

3 injections

4 injections

Please state why:

\_\_\_\_\_

\_\_\_\_\_

\_\_\_\_\_

5 Did the dose window show '0' when you finished your injection(s), as shown below?

Injection 1

 Yes No

[figure not shown]
Injection 2

 Yes No

Injection 3

 Yes No

Injection 4

 Yes No

6 Do you believe that a full dose was injected?

Injection 1

 Yes No

Injection 2

 Yes No

Injection 3

 Yes No

Injection 4

 Yes No

If you answered "No" in question 6 above:

7 At what step(s) did the problem occur?

- Preparing the pen
- Priming the pen
- Setting the dose
- Injecting
- After injection
- Other

Please give a brief description of the problem:

\_\_\_\_\_

\_\_\_\_\_

\_\_\_\_\_

*Thank you for your participation.*

Effective Date: Date of final electronic approval

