## APPENDIX N: OBSERVER ASSESSMENT TOOL (OAT)

### Observer Questionnaire

#### Introduction to the assessment

Start the assessment by handing the study materials as outlined in the Subject Study Medication Dosing Booklet and Instructions to the subject or caregiver (user), after they have been trained as outlined in the protocol.

Inform the user that there is no need to hurry. There is no benefit to achieving a shorter time. Doing the procedure CORRECTLY is most important—not speed.

Inform the user that you are there to observe and provide guidance and the onus is on the user to be able to perform the injection without physical assistance. A reason for your physical intervention may be for example to prevent an avoidable injury.

The user should read or refer to the Instructions for Use (IFU)—as much as needed.

If splitting the dose between 2 different pens please complete a new questionnaire for each pen.

In some cases more than 1 injection from the same pen may be needed.

Please record all injections from the same pen on this questionnaire.

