#### In the event of an unsuccessful injection

If the pre-filled pen fails to operate, or if the user cannot use the pen so that the injection cannot be performed, document this as a failure in the form (on next page) and provide the user with another pen, but do not provide physical assistance.

Record the injection with the replacement pen on a fresh observer questionnaire. A pen failure should be dealt with as a device complaint (see Protocol Medical Device Complaint Reporting Requirements).

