#### Providing assistance to the user

If the user is able to successfully administer the dose but requires your help to complete the injection, document the specifics below, including asking the user if after the injection they are now confident that they will be able to inject unassisted at home.

If not, provide additional training until you have addressed their confusion or concerns and they confirm their understanding as to how to successfully administer the study drug.

Turn over for questions 

Effective Date: Date of final electronic approval

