### Observer Questionnaire

Turn over for instructions 

Subject ID

Assessment date

Pen kit number

Signature:

**1** Based on your observations, did the user successfully inject into an acceptable injection site? Please report all injections from this pen.

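### The OAT success rule in Section 8.6.4 cites a question about unaided injection that the Appendix N form does not ask, so physically assisted injections can be scored as successes

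*Protocol*

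**What the plan says.** The OAT endpoint is listed in Protocol Section 8.4.5, in a line that begins "Proportion of successful single injections out of total number of single injections using the MOD-4023 PEN in US patients at Wk 1, based on the" and ends by naming the tool. It is summarised descriptively.

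Section 8.6.4 gives the scoring rule. It names one question, "did the user successfully inject into an acceptable injection site without physical assistance", and then says: "The single injection is considered successful if the observer answers" Yes to it for all attempts on the form. No other item enters the rule.

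Appendix N contains the form. Question 1 reads "Based on your observations, did the user successfully inject into an acceptable injection site" and is answered Yes or No for each injection. The instructions that accompany it say three relevant things:

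- In the introduction, the observer is to tell the user that "the onus is on the user to be able to perform the injection without physical assistance".
- If the pen fails or the user cannot use it, so that the injection cannot be performed, the observer is to "document this as a failure in the form (on next page) and provide the user with another pen, but do not provide physical assistance".
- On assistance: "If the user is able to successfully administer the dose but requires your help to complete the injection, document the specifics below".

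The synopsis (Statistical Analysis) defers details of the success criteria to the SAP. The SAP supplied covers the open-label extension only and does not mention the OAT.

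**The concern.** The analysis section presents its question as the form's question, but the two differ in the condition that defines the endpoint. Section 8.6.4 describes unaided use. The printed item asks only whether the user injected successfully into an acceptable site. An observer who had to step in physically has no instruction on how to answer it, and the form's own language calls such a dose successfully administered.

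Demonstrating successful single-injection operation of the PEN is one of the secondary objectives in Section 2. The OAT is the part of that evidence in which a third party watches a user operate the pen: the Participant Assessment Tool (PAT) is self-reported, and inspection of returned devices tests the device, not its use. If assisted injections are mixed in, a reader who relies on Section 8.6.4 would take the proportion as a measure of unaided use when it may not be one. Observers may also resolve the ambiguity differently, so the figure could mix two definitions.

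**Working it through.** The plan states no expected success rate, sample size or test for this endpoint, so there is no figure to reproduce. The check is to set the two wordings side by side for each outcome an observer could meet at Visit 2.

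| Outcome | Question as cited in 8.6.4 | Question 1 as printed | What Appendix N tells the observer |
|---|---|---|---|
| Completed unaided | Yes | Yes | Nothing further |
| Completed after verbal guidance only | Yes (guidance is not physical assistance) | Yes | Document the specifics, if regarded as help |
| Completed with physical assistance | No | Not settled; Yes is a natural reading | Dose described as successfully administered; document the specifics |
| Could not be performed | No | No | Record a failure; new pen, new form |

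Only the third row differs. Three features of the text point towards Yes in that row. The printed question uses the same idea of success that the assistance instruction applies to a helped dose. The failure instruction is reserved for injections that cannot be performed. Nothing tells the observer to mark No after helping.

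The direction of the error follows from the same table. Let *n* be the single injections scored, *a* those completed without physical assistance and marked Yes, and *h* those completed with physical assistance and marked Yes.

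- Proportion under the rule applied to the printed form: (*a* + *h*) / *n*
- Proportion under the definition described in 8.6.4: *a* / *n*
- Difference: *h* / *n*, which is zero or positive

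The reported proportion can equal the unaided rate or exceed it, but cannot fall below it through this mechanism. The value of *h* depends on how often physical assistance is given and how observers then mark question 1. The documents give neither, so no magnitude is derived.

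**The case against.** The strongest reply is that the intention is clear and the observer has been told it. The Appendix N introduction puts the onus on the user to inject unaided, gives preventing an avoidable injury as an example of a reason to intervene physically, and describes the observer's role as watching and guiding. An observer who follows that closely might mark No after physical help. This stands to the extent that scoring assisted injections as successes is a possibility left open, not a stated rule. A reader might infer that every helped injection is counted as a success; the form does not say so.

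The help referred to in the assistance instruction may also be verbal. That stands too: Section 8.6.4 excludes only physical assistance, so a verbally guided injection is properly a success, and the overstatement cannot be equated with the share of injections completed with any help.

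The end of the form is missing from the review copy and the main-study SAP was not supplied. Either may contain a separate assistance item or a fuller criterion. This limits certainty about what is recorded. It does not repair Section 8.6.4, whose rule uses one question only.

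A reader might extend the point to the PAT, which asks "Who actually gave the injection" and whether help was needed but scores neither. The documents do not support treating that as the same defect. The PAT rule rests on the dose window and on belief that a full dose was given; it never claims unaided use.

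Finally, the stated objective speaks of successful operation and does not say unaided, and the endpoint is descriptive. Both are fair limits on importance, but the unaided condition is the plan's own, in its own scoring rule.

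**Conclusion.** The mismatch is real and should be corrected. Section 8.6.4 defines success through a condition that the scored item omits, and Appendix N leaves open how a physically assisted injection is marked. Physically assisted injections can be counted as successes, so the OAT proportion may overstate unaided use, by an amount the documents do not allow one to estimate.

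The conclusion on direction assumes that unaided successes are marked Yes and injections that could not be performed are marked No under either wording, as the table shows. It also assumes that no unseen text changes the scoring rule. The effect is limited to one descriptive endpoint in USA MOD-4023 patients at Week 1. The non-inferiority analysis of height velocity does not use it.

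**What to change.** In Section 8.6.4:

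- Define OAT success as Yes to question 1 for all attempts on the form **and** no physical assistance documented for that injection. Appendix N already asks for the specifics of help.
- State that verbal guidance alone does not count as physical assistance.
- Report injections completed with physical assistance as a separate row, counted as not successful.

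On forms not yet used, align question 1 with Section 8.6.4. Apply the same combined rule to old and new forms so that their answers can be pooled. If the main-study SAP or the end of the form already holds an assistance item, the rule should cite it.

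The cost is a few sentences of analysis text, one table row and a small form revision. The specifics on completed forms would have to be classified as physical or verbal help before they are summarised. The reported success rate may be slightly lower.

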#### Quality of Life Questionnaire

The 3 dimensions (physical, social, and emotional) of the QoLISSY questionnaire will be calculated individually and as a combined core total score based on the QoLISSY scoring manual. This core score is calculated as the sum of the means of these 3 dimensions and divided by 3. All scores will be transformed from raw scores to 0 to 100 scores.

#### 8.6.5 LT-OLE Analysis

During the LT-OLE the primary goal of this safety and efficacy analysis is to report on the effect of long-term treatment on Annual HV and other auxological/clinical and biochemical measures.

- Annual HV will be summarized with descriptive statistics each year of LT-OLE treatment. For patients who discontinue without annual measurement, their HV will be calculated based on their last available measure.
- Change in Ht SDS every 12 months (the last value within each year compare to the value 12 months earlier) will be summarized with descriptive statistics.
- Change in bone maturation (BM) every 12 months, (compared to Week 52 BA (calculated as BA/CA) at completion of LT-OLE year 1 and to previous values from LT-OLE year 2 onwards).
- IGF-1, IGF-1 SDS, IGFBP-3 and IGFBP-3 SDS will be summarized with descriptive statistics at each visit. A summary of the incidence of IGF-1 SDS >2.0 at each visit will be provided.

### 8.6.6 Safety Analysis

The assessment of safety will be based mainly on the frequency of treatment emergent AEs and on the number of laboratory values that fall outside of pre-determined ranges. Data of all safety endpoints will be listed and tabulated.

#### **LT-OLE:**

The assessment of safety will be based mainly on the frequency of treatment emergent AEs and on the number of laboratory values that fall outside of pre-determined ranges. Each of the listed safety endpoints will be summarized with descriptive statistics for each year and overall. Data of all safety endpoints will be listed.

### 8.6.7 Adverse Events

AEs will be coded with Medical Dictionary for Regulatory Activities (MedDRA).

For analysis purposes, all AEs will be classified to the appropriate MedDRA preferred term (PT) and system organ class (SOC). For each patient, multiple events that map to the same PT will only be counted once for the PT, and multiple PTs within an SOC will only be counted as 1 occurrence for that SOC to assess patient incidence of events by PT and SOC. The count and percentage of patients with each PT and SOC will be summarized for each treatment group.

Relationship and severity of AEs will be summarized (patient count, % of patients) for each treatment group. For these summaries, multiple occurrences of an event within a patient will be classified as a single observation with the strongest relationship and maximum severity ratings. In addition, frequency tables of all reported events with each associated relationship and severity will be presented.

SAEs will be classified as SAEs by the investigator and will be summarized by treatment group, PT and SOC, as well as total patients exposed.

### 8.6.8 Clinical Laboratory Findings

Any CS laboratory data will be reported as an AE. Laboratory data will be reported by analyte for each treatment group. There will not be any hypothesis testing. The laboratory results will be presented at each visit along with the raw change from Baseline for quantitative data. Presence/absence or normal/abnormal results will be summarized as count and percentage. In addition, shift tables summarizing changes from normal to out-of-normal range will be provided.

Descriptive statistics (the number and percentage of patients) of patients with the presence of anti-r-hGH and anti-MOD-4023 Abs will be summarized.

### 8.6.9 Vital Signs, Fundoscopy and ECG

Any CS findings will be reported as an AE. The summary of abnormal findings at each visit will be displayed by treatment group. Descriptive statistics of vital signs will be calculated at each scheduled visit and will include the raw change from Baseline.

## 9. ETHICS

### 9.1 INSTITUTIONAL REVIEW BOARD OR INDEPENDENT ETHICS COMMITTEE

Prior to initiation of the study, the PI will submit the study protocol and amendments, sample ICF and any other documents that may be requested to the IRB/IEC for review and approval. The Investigator will request that the IRB/IEC provide written approval of the study and will keep on file records of approval of all documents pertaining to this study. The Investigator will not begin the study until the protocol and ICF have been approved by the IRB/IEC. The Investigator must agree to make any required progress reports to the IRB, as well as reports of SAEs, life-threatening conditions, or death.

### 9.2 ETHICAL CONDUCT OF THE STUDY

All clinical work conducted under this protocol is subject to GCP guidelines. This includes an inspection by Sponsor or its designee, health authority or IRB/IEC representatives at any time. The Investigator must agree to the inspection of study-related records by health authority representatives and/or Sponsor or its designee.

The study will be conducted in accordance with Sponsor's standards operating procedures (SOPs) and the following guidelines:

- GCP: International Council for Harmonization (ICH): Integrated Addendum to ICH E6 (R1): Guideline for Good Clinical Practice E6 (R2), 09 November 2016.
- Declaration of Helsinki: Brazil, 2013 ([Appendix G](#)).
- Local country guidelines for conducting clinical studies.

### 9.3 PROTOCOL REVISIONS AND/OR DEVIATIONS

Changes to the protocol may be made only by the Sponsor (with or without consultation with the investigator). All protocol modifications must be submitted to the IRB/IEC in accordance with local requirements and, if required, to RAs, either as an amendment or a notification. Approval for amendments must be awaited before any changes can be implemented, except for changes necessary to eliminate an immediate hazard to study patients, or when the changes involve only logistical or administrative aspects of the study. No approval will be required for notifications.

### 9.4 PATIENT INFORMATION AND CONSENT

Prior to screening for the study each patient and parent(s)/legal guardian will be informed in detail about the study drugs to be administered and the nature of the clinical investigation with its risks and discomforts to be expected. The basic elements of informed consent as specified by the FDA (21 CFR 50.25) and ICH-GCP will be followed.a Written consent will be obtained from each patient to be involved in the clinical study by using the IRB/IEC-approved ICF prior to the conduct of any study-related activity. Each patient will be given a copy of the written ICF. The patients will also be instructed that they are free to withdraw their consent and discontinue their participation in the study at any time without prejudice. Each patient's chart will include the signed ICF for study

---

a Illiterate patients should provide their consent in a method that is accepted according to local regulations.

participation. When the study treatment is completed and the eCRF has been monitored, the ICF will be kept in the Investigator's Site File for the required period of time. RAs may check the existence of the signed ICF in this central study folder if not having done so during the study.

Children and adolescents are legally unable to provide informed consent to participate in clinical studies. Informed consent must be obtained instead from the legally acceptable representative of the child or adolescent, usually their parent(s) or legal guardian. However, children and adolescents should be involved in health-care decisions affecting them. To that end, ICH guidelines, EMA Guideline on the Ethics of Clinical Trials in Children and FDA regulations require that the assent from the child or adolescent be obtained when this is appropriate and when the potential patient is capable of providing assent. The determination of appropriateness and capacity of children in the study to provide assent is made by the relevant IRB/EC, though it may be left to the investigator to assess whether assent is actually obtainable from children of a young age, such as preschool-aged children.

Assent may not be required if, consistent with local law and regulatory requirements, the IRB/EC determines that the intervention or procedure involved in the research holds out a prospect of direct benefit that is important to the health or well-being of the potential patients and is available only in the context of the research. Even where the IRB/EC determines that patients are capable of assenting, the IRB/EC may still waive the assent requirement under special circumstances. Where parental permission is to be obtained, the IRB/EC may find that permission of 1 parent is sufficient if consistent with local law and regulatory requirements. For clinical investigations involving greater than minimal risk, permission is generally required from both parents unless only 1 parent has legal custody, or one parent is deceased, unknown, incompetent, or not reasonably available.

